2.6. Study Rationale

Currently, there is no approved and effective targeted therapy for treatment of AIHA. Despite current treatment algorithms, there is a significant morbidity and mortality rate, and disease relapse remains an ongoing challenge for a significant number of patients with AIHA. Therefore, there remains an unmet need for new treatments for AIHA. In addition to showing efficacy in a number of B-cell—related cancers, treatment with INCB050465 has shown significant improvement in animal models of AIHA and lupus nephritis, as well as other antibody-mediated diseases. INCB050465 may represent an alternative treatment for participants who have failed at least 1 prior treatment. INCB050465 may be a more flexible intervention, as current therapy with rituximab results in profound and sustained depletion of circulating B cells.

The length of treatment in this study is 12 weeks with an observational follow-up of 12 weeks (3 months), as AIHA tends to follow a course of remission/relapse following conventional therapies. The length of treatment is expected to allow for recovery of hemoglobin and evaluation of hemolytic markers, as well as permit initial safety assessment. Participants with warm, cold (CAD), and mixed-type AIHA who have failed at least 1 prior treatment for AIHA will be eligible for enrollment. To mirror the relative incidence of warm, mixed, and cold (CAD) disease, which is about 80% warm AIHA patients and about 20% of mixed and CAD patients, a minimum of 7 patients with warm AIHA will be enrolled in Cohort 1, and the remaining patients may be CAD or mixed, or the cohort may be completed with warm AIHA patients as available. Cohort 2 (n \approx 15) distribution and increased number of participants are intended to better evaluate CAD AIHA patients and possible signal observed in Cohort 1, as well as account for higher baseline variability seen in the wAIHA subpopulation. Cohort 2 will have approximately 5 CAD AIHA participants and up to 8 wAIHA participants; the remainder can be wAIHA, CAD, or mixed-type AIHA. As corticosteroid treatment plays an important role in management of the disease, participants will be permitted to continue on a low dose (equivalent to ≤ 20 mg/day of prednisone) of corticosteroids or taper corticosteroids as appropriate. The

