3. OBJECTIVES AND ENDPOINTS

Objectives	Endpoints					
Primary						
To evaluate the efficacy of INCB050465 in the treatment of participants with AIHA.	• Proportion of participants attaining a CR (defined as hemoglobin >12 g/dL not attributed to transfusion effect* and the normalization of hemolytic markers) at any visit from Week 6 to Week 12.					
	 Proportion of participants attaining a PR (defined as hemoglobin 10-12 g/dL or at least ≥ 2 g/dL increase from baseline not attributed to transfusion effect and the normalization of hemolytic markers) at any visit from Week 6 to Week 12. 					
	*No transfusion effect definition: > 1 week since last transfusion.					
To evaluate the safety of INCB050465 administered as repeat doses in participants with AIHA.	Safety and tolerability will be assessed by monitoring AEs, measuring vital signs and ECGs, and conducting clinical laboratory blood and urine sample assessments.					
Secondary						
To further evaluate the efficacy of INCB050465 in the treatment of participants with AIHA.	 Proportion of participants attaining a CR during postbaseline visits. 					
	Proportion of participants attaining a PR during postbaseline visits.					
	 Proportion of participants attaining a ≥ 2 g/dL increase in hemoglobin from baseline. 					
	Mean, change, and percentage change from baseline of hemoglobin.					
	Proportion of participants requiring transfusions.					
	Proportion of participants who achieve normalization of hemolytic markers. (Hemolysis markers: hemoglobin, haptoglobin, LDH, reticulocyte count, total bilirubin, and direct/indirect bilirubin.)					
	Change of daily usage of prednisone.					
	FACIT-F sub-scale assessment.					
To evaluate the PK effects of INCB050465.	PK endpoints: C _{max} , t _{max} , C _{min} , AUC _{0-t} , and CL/F.					
To evaluate the PD effects of INCB050465.	Change from baseline in PD markers: reticulocyte count, DAT for IgG and C3b, cold agglutinin levels, haptoglobin, total bilirubin, direct/indirect bilirubin, LDH, and complement assessment (CH50, C3, and C4).					

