5.1. Inclusion Criteria

A participant who meets all of the following criteria may be included in the study:

- 1. Men or women, aged 18 years or older.
- 2. Diagnosis of AIHA based on the presence of hemolytic anemia and serological evidence of anti-erythrocyte antibodies, detectable by the DAT as follows:
 - a. Warm: DAT positive for IgG only or IgG plus C3d
 - b. Cold (CAD): DAT positive for C3d only, with cold agglutinins of I specificity
 - c. Mixed: DAT positive for IgG and C3d, with coexistence of warm autoantibodies and high titer cold agglutinins
- 3. Participants who have disease progression after treatment with standard therapies that are known to confer clinical benefit or who are intolerant to treatment. There is no limit to the number of prior treatment regimens.
- 4. Hemoglobin 7 to 10 g/dL (as determined by local laboratory).
- 5. No evidence of a lymphoproliferative malignancy or other autoimmune-related underlying conditions (eg, systemic lupus erythematosus, Castleman's disease, Sjögren's syndrome, or other autoimmune diseases).

- 6. ECOG performance status score of 0 to 2 (see Appendix C and Oken et al 1982).
- 7. Willingness to avoid pregnancy or fathering children based on the criteria below:
 - a. Woman of nonchildbearing potential (ie, surgically sterile with a hysterectomy and/or bilateral oophorectomy OR postmenopausal, defined by last menstrual period > 12 months before screening and confirmed by FSH).
 - b. Woman of childbearing potential who has a negative serum pregnancy test at screening and who agrees to take appropriate precautions to avoid pregnancy (with at least 99% certainty) from screening through at least 93 days after the last dose of study drug. Permitted methods that are at least 99% effective in preventing pregnancy (see Appendix A) should be communicated to the participant and her understanding confirmed.
 - c. Man who agrees to take appropriate precautions to avoid fathering children (with at least 99% certainty) from screening through at least 93 days after the last dose of study drug. Permitted methods that are at least 99% effective in preventing pregnancy (see Appendix A) should be communicated to the participant and his understanding confirmed.
- 8. Able to comprehend and willing to sign an ICF.
- 9. Willingness to receive PJP prophylaxis during the study period.

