6.6. Dose Modifications

6.6.1. Criteria and Procedures for Dose Increases of Study Drug

At Week 6, participants may be eligible for a dose increase. Due to the need to receive clinical laboratory results and to consult with the sponsor as needed prior to increasing the dose, investigators may implement the dose increase either at an unscheduled drug dispensing visit between the Week 6 and Week 8 visits or at the scheduled Week 8 visit. Any other requests for dose increase at alternate times may be considered on an individual basis in consultation with the sponsor. Individual participants in Cohort 1 may increase from INCB050465 1 mg QD to 2.5 mg QD with sponsor preapproval in the following circumstances, provided that protocol eligibility criteria are met at the time of escalation:

- Dose increase criteria, defined as the following:
 - The participant continues to require transfusions by the Week 6 visit or
 - The participant does not attain a meaningful clinical response (at least a stabilization ≥ 2 g/dL increase in hemoglobin from baseline to Week 6).
- The investigator determines there has not been a clinically meaningful response in hemoglobin and other hemolysis parameters.
- The participant is otherwise tolerating the current dose and has not had any drug-related adverse events.
- In the opinion of the investigator, the participant does not have a concurrent condition or circumstance that would complicate the dose escalation or PK sampling, or pose an increased risk.

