7.2. Efficacy Parameters

A CR for a given visit is attained if the following 2 conditions are satisfied:

1. Hemoglobin ≥ 12 g/dL.
2. Last transfusion occurred > 1 week before the date of visit.

A PR for a given visit is achieved if the following 2 conditions are satisfied:

1. Hemoglobin 10-12 g/dL or ≥ 2 g/dL increase from baseline.
2. Last transfusion occurred > 1 week before the date of visit.

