7.3. Analysis of Primary Efficacy Parameters

The primary endpoints include:

1. Proportion of participants attaining a CR at any visit from Week 6 to Week 12 and
2. Proportion of participants attaining a PR at any visit from Week 6 to Week 12

The primary endpoints will be summarized using descriptive statistics.

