10.1. Changes to Protocol-Defined Analyses

A portion of the primary endpoints that relate to hemolysis factors was removed as well as a change in the range for hemoglobin. This is a change from the Protocol in order to react to the evolving regulatory interactions and more useful information from other developments in this area.

The addition of the treatment extension evaluable population is for analysis of participants who enrolled into the open-label extension period.

An interim analysis was added for when all participants have complete Week 12 treatment. This change from the Protocol was made to support publications and a possible Phase 3 development plan for CAD participants.

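### The lower limit of partial response (10 g/dL) meets the upper limit of eligibility, so the rise needed for a primary PR shrinks to zero as baseline approaches 10 g/dL

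*SAP*

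**What the plan says.** Protocol 5.1, criterion 4, admits participants with "Hemoglobin 7 to 10 g/dL (as determined by local laboratory"). SAP 7.2 gives PR two alternative hemoglobin routes, "Hemoglobin 10-12 g/dL or ≥ 2 g/dL increase from baseline", and one further condition, "Last transfusion occurred > 1 week before the date of visit". The first route asks for a level, not a change. SAP 7.3 makes the primary endpoint "Proportion of participants attaining a PR at any visit from Week 6 to Week 12". Protocol Table 1 schedules four such visits (Weeks 6, 8, 10 and 12), and no confirmation is required.

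Protocol Section 3 has the same two routes but adds a marker condition: "increase from baseline not attributed to transfusion effect and the normalization of hemolytic markers) at any visit from Week 6 to Week 12". SAP 10.1 declares the change: "A portion of the primary endpoints that relate to hemolysis factors was removed as well as a change in the range for hemoglobin". It does not discuss the overlap with eligibility that remains.

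Protocol 6.6.1 lists, among its Week 6 criteria for a dose increase in Cohort 1: "The participant does not attain a meaningful clinical response (at least a stabilization ≥ 2 g/dL increase in hemoglobin" from baseline to Week 6).

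**The concern.** A participant who enters at 10.0 g/dL and does not change, or enters at 9.8 and reads 10.0 once, is a primary-endpoint responder. Under the protocol definition the hemolytic markers also had to normalize, which guarded against this. Without that condition, nothing in the level-based route separates improvement from ordinary visit-to-visit variation near the entry limit, and four visits give four chances.

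The study is open-label with no control arm, so the CR and PR proportions are the primary efficacy evidence. SAP 10.1 says the added interim analysis is to support publications and a possible Phase 3 plan in CAD. If the PR proportion moves with the share of participants entering at 9 to 10 g/dL, it can differ between cohorts or AIHA types for reasons unrelated to the drug. The two cohorts are designed with different mixes of AIHA type.

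**Working it through.** **The plan's own figure.** The plan states no expected, null or target response rate. Its only computed design figure is the chance of seeing at least one adverse event at a 20% rate: 1 − 0.8^10 = 0.893 and 1 − 0.8^15 = 0.965, which match the stated > 89% and > 96%. They do not bear on PR.

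**Step 1: smallest qualifying rise (no assumptions).** Inputs: entry range 7 to 10 g/dL (Protocol 5.1) and the two PR routes (SAP 7.2). Smallest rise = min(2, 10 − baseline).

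| Baseline (g/dL) | Smallest rise giving PR (g/dL) |
|---|---|
| 7.0 to 8.0 | 2.0 |
| 8.5 | 1.5 |
| 9.0 | 1.0 |
| 9.5 | 0.5 |
| 9.8 | 0.2 |
| 10.0 | 0 |

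**Step 2: chance of PR with no drug effect, by true level m.** The within-person SD is assumed. For four independent visits, P(at least one ≥ 10) = 1 − Φ((10 − m)/SD)^4.

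- m = 9.5, SD 0.3: 1 − 0.952^4 = 0.18
- m = 9.5, SD 0.5: 1 − 0.841^4 = 0.50
- m = 9.5, SD 0.8: 1 − 0.734^4 = 0.71
- m = 10.0, any SD: 1 − 0.5^4 = 0.94, against 0.50 for a single visit

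Correlation between visits lowers these. At correlation 0.5 and m = 10.0 the figure is 1 − 1/5 = 0.80. At SD 0.5, the range from correlation 0.5 to independence is 7–9% at baseline 9.0, 37–50% at 9.5, 65–82% at 9.8, and about 0% at 8.0 or below.

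**Step 3: averaged over entry levels (simulation, no drug effect, no transfusion exclusions).** Lower model: baseline uniform on 7 to 10 and equal to the true level, visits correlated 0.5. Higher model: true level uniform on 6 to 11.5, noisy observed baseline kept if 7 to 10, visits independent.

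| Assumed SD (g/dL) | PR, lower model | PR, higher model | Rise ≥ 2 only, higher model | PR at two consecutive visits, higher model |
|---|---|---|---|---|
| 0.3 | 8% | 12% | 0% | 5% |
| 0.5 | 14% | 20% | 1% | 8% |
| 0.8 | 22% | 33% | 11% | 13% |

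For about 25 participants, SD 0.5 gives 25 × 0.14 = 3.5 to 25 × 0.20 = 5 such PRs. Among entrants at 9 to 10 g/dL, the higher model gives 34%, 51% and 62% for the three SDs.

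**Step 4: would disallowing the 10–12 route at baseline ≥ 10 be enough?** With values rounded to 0.1 g/dL, the higher model falls only from 13.9% to 11.2%, 21.7% to 19.1% and 35.2% to 32.9%. Under the lower model's assumptions the fall is about 1 to 1.5 points.

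**Step 5: SAP 7.2 beside Protocol 6.6.1.** Take a Cohort 1 participant at 9.0 who reads 10.5 at Week 6, a rise of 1.5. SAP 7.2 makes this a primary PR; the 6.6.1 criterion describes the same participant as lacking a meaningful response. This can happen at any baseline above 8 g/dL. SAP 5.2 summarizes by initially assigned dose, so a participant whose dose was then increased would still count as a 1 mg PR.

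**The case against.** **The analyses are descriptive.** Protocol 10.3 tests no efficacy hypothesis, and SAP 7 calls every efficacy analysis exploratory. This stands. There is no type I error to inflate; the harm is a PR proportion that is hard to interpret.

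**Much of the information is already planned.** SAP 7.4 keeps the ≥ 2 g/dL rise, hemoglobin change and marker normalization as secondary endpoints, with Tables 2.2.2, 2.2.3, 2.2.4 and 2.2.6 and Listing 2.1. This stands in part. The ≥ 2 g/dL endpoint states neither the Week 6–12 window nor the transfusion condition, and no table shows how many primary PRs lack a 2 g/dL rise.

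**The change was declared.** It was, with a reason given. A reader might infer an undisclosed loosening, but SAP 10.1 rules that out. The 10–12 route was already in the protocol; removing the marker condition exposed the overlap.

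**Protocol 6.6.1 serves another purpose.** A reader might infer a flat contradiction. The documents do not support that: 6.6.1 is a permissive Week 6 trigger for one cohort, subject to investigator judgment and sponsor preapproval, while PR is an analysis category over Weeks 6 to 12. The tension is real, but the instructions are not incompatible.

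**Relapsing disease.** A reader might take Protocol 2.6, "AIHA tends to follow a course of remission/relapse following conventional therapies", as evidence of spontaneous swings. It describes the course after conventional treatment, so the argument here does not rely on it.

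**The simulated rates rest on assumptions.** SD, correlation and baseline distribution are all assumed. The higher model lets up to about 11% of entrants have a true level above 10. Hence the ranges; Step 1 does not depend on them.

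**Conclusion.** The overlap is established by the text alone: the rise that earns a primary PR falls from 2 g/dL at baseline 8 or below to nothing at 10.0, and one visit is enough. A reader might infer that PR requires no improvement from anyone; that goes too far, because entrants at 8 g/dL or below still need the full 2 g/dL. The effect is concentrated at 9 to 10 g/dL, which makes the proportion sensitive to case mix.

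The likely size is 8–12%, 14–20% or 22–33% PR without any drug effect, for assumed SDs of 0.3, 0.5 and 0.8 g/dL. These figures assume baselines spread over 7 to 10 and leave out transfusion exclusions, which would lower them. At SDs of 0.3 and 0.5, nearly all of these PRs come through the 10–12 route. Because all efficacy analyses are descriptive and the change was declared, this is a point to fix before reporting rather than a fatal one.

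**What to change.** Keep the SAP 7.2 definition if the sponsor wishes, but show what it contains:

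1. Split Table 2.1.2 into (a) rise ≥ 2 g/dL and (b) 10–12 g/dL with a rise below 2 g/dL. Count a participant with qualifying visits of both kinds under (a).
2. Add a supportive row requiring a rise ≥ 2 g/dL at a Week 6–12 visit more than one week after transfusion.
3. Add a row requiring the PR criterion at two consecutive scheduled visits in Weeks 6 to 12.
4. Optionally, do not count the 10–12 route when baseline is ≥ 10 g/dL. This removes the zero-change case, but is minor and does not repair the overlap by itself.
5. Reconcile Protocol 6.6.1 with SAP 7.2, or explain in the report why the same Cohort 1 participant can be described differently. Which clinical rule is right is not a matter for this review.

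The cost is some SAP wording and a few table rows from data already collected, with no new visits. The PR proportion may read less favorably once split.

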7.3. Analysis of Primary Efficacy Parameters

The primary endpoints include:

1. Proportion of participants attaining a CR at any visit from Week 6 to Week 12 and
2. Proportion of participants attaining a PR at any visit from Week 6 to Week 12

The primary endpoints will be summarized using descriptive statistics.

7.4. Analysis of Secondary Efficacy Parameters

The secondary endpoints include:

1. Proportion of participants attaining a CR during postbaseline visits.
2. Proportion of participants attaining a PR during postbaseline visits.
3. Proportion of participants attaining a ≥ 2 g/dL increase in hemoglobin from baseline.
4. Mean, change, and percentage change from baseline of hemoglobin.
5. Proportion of participants requiring transfusions, defined as "Yes" if the last transfusion is within 7 days of the visit date and "No" otherwise.
6. Proportion of participants who achieve normalization of hemolytic markers (hemolysis markers: hemoglobin, haptoglobin, LDH, reticulocyte count, total bilirubin, and direct/indirect bilirubin).
7. Daily usage of prednisone.
8. FACIT-F subscale assessment.

All secondary endpoints will be summarized using descriptive statistics.

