Cohort 1: INCB050465 1 mg QD for up to 12 weeks. At Week 6, participants who fulfill dose increase criteria (see definition below) will be offered INCB050465 2.5 mg QD for up to 6 weeks. If there are any tolerability issues in individual participants who received 2.5 mg, the dose may be decreased to 1 mg.

[figure not shown]
Cohort 2: INCB050465 2.5 mg QD for up to 12 weeks. If there are any tolerability issues in individual participants, the dose may be decreased to 1 mg.

Criteria for dose increase: (1) Continue to require transfusions by Week 6 visit, or (2) do not attain a meaningful clinical response (at least a stabilization ≥ 2 g/dL increase in hemoglobin from baseline to Week 6). Dose increases require sponsor preapproval (see Section 6.6).

Participants who complete the 12-week treatment period and continue to receive clinical benefit from study drug may enter into an extension period with sponsor approval to continue receiving INCB050465 until the drug is available through another clinical study, or is commercially available, or the sponsor stops the study or the study drug development.

The study design is shown in Figure 1 below.

Figure 1: Study Design Schema

- ^a Cohort 1: N = 10; no more than 3 CAD or mixed-type AIHA participants.
- b Cohort 2: N = approximately 15, with approximately 5 CAD AIHA and up to 8 wAIHA participants; the remainder can be wAIHA, CAD, or mixed-type AIHA participants.

 Participants in Cohort 2 may begin enrollment after enrollment of a minimum of 6 wAIHA participants in Cohort 1 and review of safety and efficacy through Week 6.
- ^c (1) At Week 6, participants who receive 1 mg QD study drug and who fulfill dose increase criteria* may have their dose increased to 2.5 mg QD of INCB050465 until Week 12.
 - (2) If there are any tolerability issues in individual participants who received 2.5 mg, the dose may be decreased to 1 mg.
- d If there are any tolerability issues in individual participants who received 2.5 mg, the dose may be decreased to 1 mg.
- ^c If relapse of AIHA occurs within this period, PD and clinical laboratory markers of hemolysis will be assessed, and the participants will be treated based on investigators' decision.
- * Criteria for dose increase in individual participants in Cohort 1 (see Section 6.6):
- (1) Continue to require transfusions by Week 6 visit, or
- (2) Do not attain a meaningful clinical response (at least a stabilization ≥ 2 g/dL increase in hemoglobin from baseline to Week 6).

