f Serology includes HIV, hepatitis, anti-Streptolysin antibody, and anti-phospholipid antibody tests.

g For women of nonchildbearing potential only (ie, surgically sterile with a hysterectomy and/or bilateral oophorectomy OR postmenopausal, defined by last menstrual period > 12 months before screening and confirmed by FSH).

^h For women of childbearing potential only.

¹ Ferritin, iron, and total iron-binding capacity will be tested at screening for all participants and at Week 6 if the participant has ongoing transfusions requirements during the study.

Single ECG. At screening, in the event that a single QTcF is > 470 milliseconds for males or > 480 milliseconds for females, triplicate ECG measurements may be performed.

k Hemoglobin, haptoglobin, LDH, reticulocyte count, total bilirubin and direct/indirect bilirubin are hemolytic markers will be measured. During follow-up, these hemolytic markers should be assessed if a participant becomes symptomatic or starts new treatment; relevant biomarkers should also be included.

Plasma for PK analysis will be collected predose and 1, 2, and 4 hours postdose at Weeks 2 and 8. Predose PK will be collected at Weeks 1 and 12.

Table 2: Schedule of Assessments for the Extension Period

		Extension Period			Follow-Up	
Procedure	Protocol Section	At Least Every 8-12 Weeks in Clinic	EOT Extension Period	Month 1 + 5 days	Month 2 ± 5 days	Month 3 ± 5 days (EOS)
Prior/concomitant medications	8.1.5	X	X	X	X	X
Study drug dispensing	6.1	X				
Study drug accountability and assess compliance	6.5	X	X			
AE assessment	8.3.1	X	X	X	X	X
Prophylactic treatment for PJP	6.7.1.1	X	X	X	X	X
Hematology ^{a,b}	8.2.1	X	X	X	X	X
Hemolysis markers ^a	8.2.1	X	X	X	X	X
Serum chemistries ^a	8.3.5.1	X				

^a Performed at each site as per the standard of care for participant's condition and monitoring at the investigator's discretion. Frequency to be determined by the investigator if it is necessary to monitor any other ongoing clinical condition.

^b Hematology panel will be performed at local laboratory.

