4. STUDY DESIGN

4.1. Overall Design

This is a multicenter, open-label study designed to evaluate the safety and efficacy of INCB050465 administered orally to participants with AIHA who have decreased hemoglobin and evidence of ongoing hemolysis that requires treatment intervention. Participants with primary warm, cold (CAD), and mixed-type AIHA without an underlying lymphoproliferative malignancy or autoimmune related hemolytic anemia and have failed at least 1 prior treatment for AIHA will be eligible for enrollment. Participants will be treated for 12 weeks. There are 2 cohorts in this study: Cohort 1, with up to 10 participants, with no more than 3 cold (CAD)/mixed-type AIHA participants to appropriately reflect response in the overall population, which is predominantly warm AIHA; and Cohort 2, with approximately 15 participants, with approximately 5 CAD AIHA, up to 8 warm AIHA, and the remainder from any of the 3 AIHA types. Cohort 2 distribution and increased number of participants are intended to better evaluate CAD AIHA patients and possible signal observed in Cohort 1, as well as account for higher baseline variability seen in the wAIHA subpopulation. The first cohort (Cohort 1, n = 10participants) enrolled will initially receive INCB050465 1 mg QD. At Week 6, participants who continue to require transfusions or do not attain a meaningful clinical response (at least a stabilization ≥ 2 g/dL increase in hemoglobin from baseline to Week 6) may have their dose increased, with sponsor preapproval, to 2.5 mg QD of INCB050465 until Week 12 (see Section 6.6). If there are any tolerability issues in individual participants who received 2.5 mg, the dose may be decreased to 1 mg. Following enrollment of a minimum of 6 warm AIHA participants in the first cohort and review of safety and efficacy through Week 6, Cohort 2 may begin enrollment. Participants in Cohort 2 (n \approx 15) will receive INCB050465 2.5 mg QD for 12 weeks. If there are any tolerability issues, the dose may be decreased to 1 mg. The investigator and sponsor should review and agree any dose increases or decreases. Following the last dose of INCB050465, participants will be eligible for a 12-week (3 months) follow-up for evaluation of the safety and durability of response.

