8.9.2. Additional Follow-Up Period

Participants will have additional follow-up assessments for 12 weeks (3 months) after EOT. Safety follow-up is included in this 12-week (3 months) additional follow-up period. The following information will be collected:

- The start date of new AIHA therapy.
- Type of therapy.
- Marker for hemolysis.

If the participant withdraws consent for study drug but continues in the follow-up period of the study, the above information will also be collected.

The site will also use continuing participant records to supply data on subsequent treatment regimens and disease activities in the eCRF.

For participants who receive study drug in the extension period, the safety follow-up is included in the 12-week (3-month) additional follow-up period and should occur 30 to 35 days after the last dose of study drug.

9. ADVERSE EVENTS: DEFINITIONS AND PROCEDURES FOR RECORDING, EVALUATING, FOLLOW-UP, AND REPORTING

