5. STATISTICAL METHODOLOGY

5.1. General Methodology

Unless otherwise noted, SAS® software (SAS Institute Inc, Cary, NC; Version 9.1 or later) will be used for the generation of all tables, graphs, and statistical analyses. Descriptive summaries for continuous variables will include, but not be limited to, the number of observations, mean, standard deviation, median, minimum, and maximum, and both the actual value and change and/or percentage from baseline (if available) will be analyzed. Descriptive summaries for categorical variables will include the number and percentage of participants in each category. All by-visit analyses will include the follow-up period if the data are available.

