2.2 Secondary Efficacy		
2.2.1	Summary of Participants Attaining a Complete Response by Visit	FAS
2.2.2	Summary of Participants Attaining a Partial Response by Visit	FAS
2.2.3	Summary of Participants Attaining a ≥ 2 g/dL Increase in Hemoglobin From Baseline	FAS
2.2.4	Summary of Hemoglobin by Visit	FAS

Table No.	Title	Population
2.2.5	Summary of Participants Requiring Transfusions	FAS
2.2.6	Summary of Participants Achieving Normalization of Hemolytic Markers by Visit	FAS
2.2.7	Summary of Daily Usage of Prednisone by Visit	FAS
2.2.8	Summary of FACIT-F Subscale by Visit	FAS
Safety		

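### Secondary CR/PR and marker-normalization rows run into off-drug follow-up with no rule for new AIHA therapy, so a rescued relapse is scored as response under the INCB050465 regimen

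*SAP*

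**What the plan says.** SAP 7.4 lists as its first secondary endpoint "Proportion of participants attaining a CR during postbaseline visits", with a matching item for PR. Neither has an end point. Appendix A implements the first as Table 2.2.1, "Summary of Participants Attaining a Complete Response by Visit". Tables 2.2.2 (PR), 2.2.4 (hemoglobin), 2.2.6 (marker normalization) and 2.2.8 (FACIT-F) are also by visit. SAP 5.1 then states: "All by-visit analyses will include the follow-up period if the data are available".

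The visit-level definition in SAP 7.2 has two conditions: a hemoglobin criterion, and "Last transfusion occurred > 1 week before the date of visit". SAP 5.2 reports participants overall and by the dose regimen they were first assigned.

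The protocol describes the 12 weeks after the last dose as "follow-up for evaluation of the safety and durability of response" (Section 4.1). A footnote to the Figure 1 schema reads "If relapse of AIHA occurs within this period, PD and clinical laboratory markers of hemolysis will be assessed" and leaves treatment of the relapse to the investigator. Section 8.9.2 collects "The start date of new AIHA therapy", the type of therapy and the hemolysis marker. Footnote k to Table 1 says of the markers: "During follow-up, these hemolytic markers should be assessed if a participant becomes symptomatic or starts new treatment".

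**The concern.** SAP 7.2 recognizes one outside influence on hemoglobin, recent transfusion, and excludes it. Another AIHA drug is an equally direct outside influence. It is foreseen in the protocol and dated in the eCRF, yet the SAP never uses that date. A hemoglobin recovery produced by the new drug is then credited to INCB050465.

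What is at stake is the durability reading. Follow-up is meant to show whether response lasts after dosing stops, but a response that was lost and then rescued looks the same in these rows as one that was maintained. The group seen at Months 1-3 adds to the worry. Table 1 follow-up is for participants not eligible for the extension, and those with clinical benefit may stay on drug, so the Month 1-3 rows probably contain a higher share of people likely to need another treatment.

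**Working it through.** **The plan's own figures.** The plan gives no figure for relapse, rescue or durability. Its only computed figures are the chances of seeing at least one AE at a 20% rate. They reproduce from the cohort sizes used below: 1 − 0.8^10 = 0.893 (stated as above 89%) and 1 − 0.8^15 = 0.965 (stated as above 96%).

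**Which visits are exposed (Protocol Table 1).**
- Scheduled post-baseline visits with hematology: Weeks 1, 2, 4, 6, 8, 10 and 12 (7 visits), plus Months 1, 2 and 3 (3 visits). The total is 10, and 3/10 fall in follow-up. Week 12 is the EOT visit and is not counted twice.
- FACIT-F after baseline: Week 6, Week 12 and Months 1-3. That is 5 visits, and 3/5 fall in follow-up.

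**Following one participant through the rules.**
1. The participant does not enter the extension, stops at Week 12, relapses and starts another AIHA therapy. The start date goes into the eCRF (Protocol 8.9.2).
2. At Month 3, hemoglobin is at least 12 g/dL with no transfusion in the past week. Both SAP 7.2 conditions are met, so the visit is a CR.
3. SAP 5.1 places that visit in Table 2.2.1.
4. SAP 5.2 reports it under the INCB050465 regimen first assigned.

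No SAP text interrupts this sequence.

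**By-visit and participant-level readings.** In a by-visit row, a relapse followed by rescue shows as a responder at that visit. If the endpoint wording is read as one proportion per participant, someone who responded on study drug is already counted. The added responders are then those whose only qualifying visit came after new therapy. Both readings need the same cut-off.

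**Size per participant.** With the FAS as denominator, one misattributed responder shifts a proportion by 100/n points:
- Cohort 1: 100/10 = 10.0
- Cohort 2: 100/15 = 6.7
- Overall: 100/25 = 4.0

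**Illustrative total (assumed rates).** If a share q of the FAS starts new therapy and a share s of those then meets the hemoglobin criterion, the shift is 100 × q × s points.
- q = 0.10, s = 0.30: 3 points
- q = 0.20, s = 0.50: 10 points (2.5 of 25 participants)
- q = 0.40, s = 0.70: 28 points

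These values of q and s are not in the documents, and the range shows only how the result depends on them.

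**Markers in follow-up.** Footnote k ties follow-up marker assessment to symptoms or new treatment. Section 8.9.2 lists the marker with no condition. Table 1 schedules chemistry and hematology at Months 1-3. Table 5 places haptoglobin, LDH and total bilirubin in chemistry, and hemoglobin and reticulocytes in hematology. The passages disagree about when follow-up marker values are to be obtained.

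**The case against.** The strongest reply is that the consequence is limited. All analyses are exploratory and no durability endpoint is defined. The primary endpoints stop at Week 12. In a by-visit table, a rescued participant sits in a labeled Month 1-3 row, where a reader can see that dosing had ended. All of this is true and it limits the severity. It does not remove the problem, because the row still reports a CR or PR under an INCB050465 regimen with nothing to show that another drug was on board.

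Protocol 6.7.3 might seem to prevent the situation, since it prohibits the medications named in the exclusion criteria through the safety follow-up. That is a rule of conduct and removes no data. It also sits awkwardly with the Figure 1 footnote on treating relapse, and the two passages need to be reconciled.

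Four stronger readings are tempting, and the documents do not support them:
- *The primary result is contaminated.* The follow-up rows do not reach the Week 6-12 window.
- *The ≥ 2 g/dL rise is affected in the same way.* Table 2.2.3 is not titled by visit and has no stated window, so its extension into follow-up is unspecified.
- *The follow-up marker rows rest on a symptom-selected subset.* Footnote k does not say that markers are taken only then, and the panels are scheduled for everyone in follow-up. This is a conflict of wording; selection is not demonstrated.
- *The inflation is known to be large.* No rescue rate is given, so only the per-participant step can be stated without assumption.

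**Conclusion.** The point holds for the secondary CR and PR tables (2.2.1 and 2.2.2) and for marker normalization (2.2.6). The written rules score recovery under another AIHA therapy as attainment under the assigned INCB050465 regimen, at up to 3 of 10 scheduled post-baseline visits. The by-visit hemoglobin and FACIT-F summaries mix visits before and after new therapy without distinction, which is a matter of labeling rather than a false response.

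The step of 10.0, 6.7 or 4.0 points per participant assumes that cohorts reach their planned sizes and that the FAS is the denominator. If percentages use only participants with data at the visit, each one weighs more. The conclusion about durability also assumes that some participants start new therapy in follow-up, which the protocol plainly provides for but does not quantify. This should be corrected before the follow-up rows are interpreted, but it does not threaten the primary analysis.

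**What to change.** In SAP 7.2 and 7.4:
- Score CR, PR and marker normalization as not attained at any visit on or after the start of new AIHA therapy, using the date collected under Protocol 8.9.2.
- Apply the same cut-off to any participant-level proportion over post-baseline visits.
- State the window for the ≥ 2 g/dL rise, and apply the cut-off there if follow-up is included.
- For hemoglobin and FACIT-F, keep the by-visit means but flag visits after new therapy or show them separately. Simply excluding them would drop relapsed participants and could flatter durability, particularly as SAP 4.1.4 imputes nothing in general.

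Separately, reconcile Table 1 footnote k with Protocol 8.9.2, Table 1 and Table 5, so that the follow-up marker rows use the panels already scheduled at Months 1-3.

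The cost is a few SAP sentences and one footnote clarification. The therapy dates and laboratory panels are already planned, so no new data collection is needed. The downside for the sponsor is that follow-up response figures may be lower.
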